**PSSD Item Score (0-10)**

- a. PSSD 24-hr recall, each individual item score over seven days is averaged into a weekly item score (i.e. 7 days [from day -7 to -1] prior to a visit).
- b. PSSD 7-day recall, each individual item response is used as the score.

**Symptom Score (0-100)**

- a. Symptom score includes the following items: itch (Q1), skin tightness (Q4), burning (Q9), stinging (Q10), and pain (Q11).
- b. PSSD 24-hr recall: Compute the average of the 5 weekly symptom item scores when at least 3 items are available ( $\geq 50\%$  of 5 items). Multiply the average by 10 to convert into 0-100 scoring (0-least severe, 100-most severe).
- c. PSSD 7-day recall: Average symptom items when at least 3 items ( $\geq 50\%$  of 5 items) on this scale are answered. Multiply the average by 10 to convert into 0-100 scoring (0-least severe, 100-most severe).

**Sign Score (0-100)**

- a. Sign score includes the following items: skin dryness (Q2), cracking (Q3), scaling (Q5), shedding or flaking (Q6), redness (Q7) and bleeding (Q8).
- b. PSSD 24-hr recall: Compute the average of the 6 weekly sign item scores when at least 3 items are available ( $\geq 50\%$  of 6 items). Multiply the average by 10 to convert into 0-100 scoring (0-least severe, 100-most severe).
- c. PSSD 7-day recall: Average sign items when at least 3 items ( $\geq 50\%$  of 6 items) on this scale are answered. Multiply the average by 10 to convert into 0-100 scoring (0-least severe, 100-most severe).

For the PSSD 24-hr recall, at least four non-missing days of assessments out of 7 days (either consecutive or nonconsecutive) prior to a specific visit are necessary to derive a weekly score for that visit. For select timepoints (i.e., baseline, Week 4, 8 and 16), if there are less than 4 non-missing days of assessments in the 7-day window, the most recent 4 non-missing days of assessments in the 10-day window prior to that specific visit will be used. If there are less than 4 non-missing days of assessments in the 7-day (i.e., Week 2 and 12) or 10-day (i.e., baseline, Week 4, 8 and 16) window, data are considered missing for that visit.

Meeting PSSD symptom score of 0 criteria: defined as having a PSSD symptom score of 0.

Meeting PSSD itch score  $\geq 4$ -point improvement criteria: defined as having at least 4-point improvement from baseline in PSSD itch score.

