##### **Binary Endpoint Analyses**

The binary key secondary endpoints will be analyzed using the main estimands described in section 4.3.1.2.1. Composite strategy will be used for ICEs 1, 2 and/or 4 (as applicable) where participants with those ICEs will be considered as non-responders and treatment policy strategy will be used for ICE 3 where observed data will be used. For the analysis at Week 52, participants experiencing an ICE 2 from Week 24 to Week 52 will be considered non-responders at Week 52, regardless of whether an ICE 2 occurred prior to Week 24. After the application of ICEs, participants with missing data will be imputed as non-responders. The proportions of participants achieving a key secondary efficacy response will be summarized and compared between treatment groups in the same manner as the co-primary endpoints using the appropriate stratification factors. For endpoints at or prior to Week 16, the stratification factors for randomization at baseline may be used in analyses. Geographic region may be removed as a stratification factor in CMH tests for endpoints with low response rates. For the analyses of PASI 75 at Week 52, stratification factors of PASI 90 response status at Week 24, and geographic region may be used in the analyses. A stratification factor of geographic region may be used for the analysis of PASI 90 at Week 52.

In addition, key endpoints at or prior to Week 16 (defined in 4.3.1.2.1) will be summarized and compared between treatment group among adolescent participants using a CMH test stratified by geographic region.

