**Binary Endpoints**

The same strategies for addressing ICEs for key secondary analyses (binary endpoints) will be used for other secondary binary endpoints. The proportions of participants achieving a clinical

response for the efficacy endpoints will be provided by intervention group. The p-values, difference in proportions and 95% CIs will be provided based on the same model for key secondary endpoints specified in Section 4.3.1.3.1.

In addition, PSSD sign score of 0 at Week 16 will be compared between treatment group, among adolescent participants with a baseline PSSD sign score > 0, using a CMH test stratified by geographic region.

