### **4.4.2. Analysis Methods**

In general, the efficacy analyses for exploratory endpoints will be based on FAS or randomized at Week 24 analysis set (Section 4.1). Simple descriptive summary statistics, such as n, mean, SD, median, interquartile range, minimum, and maximum for continuous variables, and counts and percentages for discrete variables will be summarized by study intervention group.

Unless otherwise specified, the treatment comparisons will be performed using the same analysis methods described in Section 4.3.2.3 for other secondary endpoints. The analysis strategy for ICEs and missing data will be handled in the same manner as other secondary analyses (section 4.3.2.3). No adjustments for multiple comparisons will be made for exploratory endpoints.

Additionally, graphical data displays may also be used to summarize the over time data if applicable.

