#### **4.4.2.13. Analyses Related to Psoriasis Symptom and Sign Diary Through Week 24**

- The change from baseline in PSSD symptom score and sign score will be summarized over time through Week 24 by treatment group.
- The proportions of participants who achieve a PSSD symptom score of 0 and sign score of 0 will be summarized over time through Week 24 among participants with a baseline PSSD symptom score  $>0$ , and baseline sign score  $>0$  respectively by treatment group. Additionally, these endpoints will be summarized over time by treatment group and age group.
- The proportion of participants who achieve a  $\geq 4$ -point improvement from baseline in PSSD itch score will be summarized over time through Week 24 among participants with baseline PSSD itch score  $\geq 4$ . Additionally, this endpoint will be summarized over time by treatment group and age group.
- The change from baseline in each PSSD individual scale score will be compared between treatment groups at Week 16.

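### The PSSD weekly score has a 10-day fallback at baseline and Weeks 4, 8 and 16 but not at Weeks 2 and 12, which can bias the Week 2 and Week 12 responder rates downward in the exploratory over-time summaries

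*SAP*

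**What the plan says.** The schedule of activities (Protocol 1.3.1) has participants complete the 24-hour-recall PSSD daily from screening through Week 16. SAP 4.3.1.1.3 turns the diary into a weekly score for each visit.

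- Base rule: "at least four non-missing days of assessments out of 7 days (either consecutive or nonconsecutive) prior to a specific visit are necessary".
- Fallback: "For select timepoints (i.e., baseline, Week 4, 8 and 16), if there are less than 4 non-missing days of assessments in the 7-day window", then "the most recent 4 non-missing days of assessments in the 10-day window prior to that specific visit will be used".
- Otherwise: with fewer than 4 days "in the 7-day (i.e., Week 2 and 12) or 10-day (i.e., baseline, Week 4, 8 and 16) window, data are considered missing".

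The handling of a missing score is set in three places.

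- SAP 4.3.1.3.1, key secondary binary endpoints: "After the application of ICEs, participants with missing data will be imputed as non-responders".
- SAP 4.3.2.3, other secondary binary endpoints: "The same strategies for addressing ICEs for key secondary analyses (binary endpoints) will be used for other secondary binary endpoints". This sentence names intercurrent events and does not mention missing data.
- SAP 4.4.2, exploratory analyses: "The analysis strategy for ICEs and missing data will be handled in the same manner as other secondary analyses".

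The affected output is in SAP 4.4.2.13: "The proportions of participants who achieve a PSSD symptom score of 0 and sign score of 0 will be summarized over time through Week 24". The itch response is summarized over time in the same way, and these responder endpoints are also shown by treatment and age group.

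**The concern.** The raw data are of the same kind at Weeks 2, 4, 8, 12 and 16, but the test for a usable score is not. Take a participant with 3 diary days in the last 7 and one more in the 3 days before that. At Weeks 8 and 16 this participant is scored and may be a responder. At Week 12, with the same diary pattern, the score is missing and, under non-responder imputation, the participant is a failure. The SAP gives no reason for the split.

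At stake is the reading of one set of curves. Part of any change from Week 8 to Week 12, or from Week 12 to Week 16, could come from the window and not from the disease, overall and within the age-group displays.

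**Working it through.** **Inputs from the documents.** At least 4 days are needed. The window is 7 days at Weeks 2 and 12, and effectively 10 days at Weeks 4, 8 and 16. Missing counts as non-response (SAP 4.3.1.3.1, reached from 4.4.2 through 4.3.2.3). The plan states no figure for diary completion, for the share of scores rescued by the fallback, or for PSSD response at Week 12, so there is no figure of its own to reproduce.

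**Assumptions.** Daily completion q of 70% to 90%; a true response rate r of 40%; completion unrelated to response. Days are taken first as independent, then as correlated within a person (beta-binomial, correlation 0.2).

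**Formulas.**
- Missing share, 7-day rule: m7 = P(at most 3 of 7 days completed).
- Missing share, 10-day rule: m10 = P(at most 3 of 10 days completed).
- Four days within 7 are also four days within 10, so m7 − m10 is exactly the share of participants that the fallback would rescue.
- Expected reported rate = r × (1 − m). Shortfall at Weeks 2 and 12 = r × (m7 − m10).

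| Completion q | Days | m7 | m10 | m7 − m10 | Shortfall at r = 40% |
|---|---|---|---|---|---|
| 90% | independent | 0.3% | 0.0% | 0.3% | 0.1 points |
| 80% | independent | 3.3% | 0.1% | 3.2% | 1.3 points |
| 70% | independent | 12.6% | 1.1% | 11.5% | 4.6 points |
| 90% | correlation 0.2 | 4.2% | 1.3% | 2.9% | 1.2 points |
| 80% | correlation 0.2 | 11.7% | 4.5% | 7.2% | 2.9 points |
| 70% | correlation 0.2 | 22.4% | 10.3% | 12.1% | 4.8 points |

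For example, 0.40 × 11.5% = 4.6 points. Clustering matters most at high completion: at 90% the shortfall rises from about 0.1 to about 1.2 points.

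**Does the curve turn down?** With true rates p8 and p12, the reported Week 12 rate falls below Week 8 only if p12/p8 < (1 − m10)/(1 − m7). For independent days the right-hand side is 1.003 at 90% completion, 1.034 at 80% and 1.132 at 70%. Two assumed curves show both outcomes:
- True rate rising from 18% to 25%: the reported rates are 18.0% to 24.2% at 80% completion and 17.8% to 21.9% at 70%. Even at 60% completion they go from 17.0% to 17.8%. There is no dip.
- Near-plateau, 25% to 25.5%: the reported rates are 25.0% to 25.4% at 90% completion (still rising), 25.0% to 24.7% at 80% and 24.7% to 22.3% at 70%. There is a dip at 80% and below.

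**Arm difference.** With equal completion in both arms the difference shrinks in proportion. An assumed 23-point difference at Week 12 reads 22.2 under the 7-day rule against 23.0 under the 10-day rule at 80% completion, and 20.1 against 22.8 at 70%.

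**The case against.** The split is deliberate and has a logic. The fallback visits are baseline plus every visit with an alpha-controlled PSSD endpoint (Weeks 4, 8 and 16), so all tested PSSD endpoints share one rule. Weeks 2 and 12 appear only in exploratory summaries. This stands, and it limits the weight of the point. It does not explain why two visits in the same 24-hour-recall series need a stricter rule.

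The imputation link is inferred. Only SAP 4.3.1.3.1 states non-responder imputation outright, and the middle step, SAP 4.3.2.3, speaks of intercurrent events alone. This also stands, so the point is conditional. The inference is still the natural one, because SAP 4.4.2 points to that section for missing data as well.

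The size rests on assumed completion. Protocol 1.3.1 and 8.1 have sites check the eDiary and retrain participants through Week 16, which favors the upper end of the range. At 90% completion with independent days the effect is negligible.

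Different completion by arm would distort non-responder imputation at every visit, so that problem is not specific to the window; the shorter window only changes its amount. The same summary also changes to 7-day recall after Week 16, so one window would not make the whole curve comparable. It would make the 24-hour-recall part comparable. Finally, Protocol 8.1 mentions only 4 days within 7, for randomization and Week 16, so a wider fallback moves further from that text. The two documents already differ there and should be reconciled in any case.

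**Conclusion.** The point holds as a minor one. If missing counts as non-response, the Week 2 and Week 12 PSSD responder rates are expected to be lower than under the rule used at Weeks 4, 8 and 16 whenever some responders have fewer than 4 of 7 but at least 4 of 10 diary days. At an assumed 40% response, the shortfall runs from about 0.1 to 1.3 points at 90% to 80% completion with independent days, from about 1.2 to 2.9 with correlation 0.2, and is near 5 points at 70% completion under either assumption.

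A reader might infer that the window rule forces the curve to dip at Weeks 2 and 12. The documents do not support that. A fall from Week 8 to Week 12 needs a near-plateau in true response, and in the examples above also completion of about 80% or lower. Week 2 is the first post-baseline visit, so there is no earlier one for it to fall below. Nor does the point extend to the change-from-baseline curves: SAP 4.3.2.3 leaves missing continuous data unimputed and relies on the MMRM. No co-primary or key secondary result is touched.

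**What to change.** In SAP 4.3.1.1.3, apply the 10-day fallback at every visit scored from the 24-hour-recall diary, adding Weeks 2 and 12. In the same edit, state in SAP 4.3.2.3 or 4.4.2 whether missing binary data count as non-response in the over-time summaries. The cost is a sentence or two and one programming parameter; the tested endpoints at Weeks 4, 8 and 16 do not change.

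The downside is small: a rescued Week 2 score draws on slightly earlier days. Those days are still after the first dose. With the first dose on Day 1 and a Week 2 visit two days early, on Day 13, the ten preceding days are Days 3 to 12. If the SAP text is left as it is, a table footnote should at least disclose the differing windows, although that leaves the bias in place.

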#### 4.3.1.1.4. Scalp Specific Investigator Global Assessment

The ss-IGA instrument is used to evaluate the disease severity of scalp psoriasis. The lesions are assessed in terms of the clinical signs of redness, thickness, and scaliness which are scored as: absence of disease (0), very mild disease (1), mild disease (2), moderate disease (3), and severe disease (4).

Meeting ss-IGA score of 0 or 1 criteria: defined as having an ss-IGA score of absence of disease (0) or very mild disease (1) and at least a 2-grade improvement from baseline.

#### 4.3.1.2. Estimands

##### 4.3.1.2.1. Main Estimands for Key Secondary Endpoints (Sec 1-14)

##### Endpoints at or prior to Week 16 (Sec 1-10)

The main estimands for key secondary endpoints at or prior to Week 16 have same attributes as co-primary estimands, except for attributes of variable and population defined in [Table 3](#).

**Table 3: List of Variables and Populations for Key Secondary Endpoints at or Prior to Week 16**

Estimands	Variable Achieving a response based on:	Population
Sec 1	IGA score of 0 at Week 16	Same population as the primary estimand specified in section 4.2.2.1
Sec 2	PASI 75 at Week 4	
Sec 3	PASI 90 at Week 8	
Sec 4	PASI 75 at Week 16	
Sec 5	PASI 100 at Week 16	
Sec 6	ss-IGA score of 0 or 1 and a $\geq 2$ grade improvement from baseline at Week 16	Patients $\geq 12$ years of age with moderate to severe plaque psoriasis and with a baseline ss-IGA score $\geq 2$
Sec 7	PSSD symptom score of 0 at Week 8	Patients $\geq 12$ years of age with moderate to severe plaque psoriasis and with a baseline PSSD symptom score $> 0$
Sec 8	PSSD symptom score of 0 at Week 16	
Sec 9	$\geq 4$ -point improvement from baseline in PSSD itch score at Week 4	Patients $\geq 12$ years of age with moderate to severe plaque psoriasis and with a baseline PSSD itch score $\geq 4$
Sec 10	$\geq 4$ -point improvement from baseline in PSSD itch score at Week 16	

As in the co-primary estimands, achieving a response based on a scale is defined as meeting the efficacy criteria based on that scale and not experiencing ICEs 1 and 2.

**Endpoints at Week 52 (Sec 11-14)**

Main question of interest is:

For adult patients with moderate to severe plaque psoriasis who are PASI 75 or IGA 0 or 1 responders at Week 24, what is the effect up to Week 52 of continuing JNJ-77242113 versus treatment withdrawal?

The main estimands for key secondary endpoints at Week 52 are defined by the following 5 attributes.

**Treatment condition of interest vs Alternative treatment condition:**

Assignment to continuation of JNJ-77242113 200 mg QD vs withdrawal group (Placebo).

**ICEs and their corresponding strategies:**

Same ICEs 1-3 as those defined in the co-primary estimands. In addition, ICE 4 is defined as meeting criteria of loss of  $\geq 50\%$  Week 24 PASI improvement. Patients with this ICE will be handled using the composite strategy.

**Variable, Population and Population Level Summary:** Refer to [Table 4](#)

**Table 4: Variables, Populations and Population Level Summaries for Key Secondary Endpoints at Week 52**

Estimands	Variable	Population	Population Level Summary
Sec 11	Achieving a PASI 75 response at Week 52	Adult patients with moderate to severe plaque psoriasis who are PASI 75 responders randomized at Week 24	Difference in proportions
Sec 12	Achieving a PASI 90 response at Week 52	Adult patients with moderate to severe plaque psoriasis who are PASI 90 responders randomized at Week 24	
Sec 13	Time to loss of PASI 75 through Week 52 (defined in Section 4.3.1.1.2 )	Adult patients with moderate to severe plaque psoriasis who are PASI 75 responders randomized at Week 24	Hazard ratio (HR) vs placebo
Sec 14	Time to loss of PASI 90 through Week 52 (defined in Section 4.3.1.1.2 )	Adult patients with moderate to severe plaque psoriasis who are PASI 90 responders randomized at Week 24	

Note: For participants experiencing multiple ICEs, ICE 2 and 4 will override an ICE 3.

**4.3.1.2.2. Supplementary Estimands for Key Secondary Endpoints**

The supplementary estimands have the same components as the main estimands for key secondary endpoints, except for the strategies used for ICEs and not counting ICEs as non-responders in the variable definition. The same Treatment Policy estimands (Section [4.2.2.2](#)) for the co-primary endpoints will be used for the following selected key secondary endpoints. Supplementary estimands are not planned for the secondary endpoints at early timepoints (i.e., Week 4, Week 8) due to the anticipated limited ICEs.

- IGA scores of cleared (0) at Week 16
- PASI 75 response at Week 16
- PASI 100 response at Week 16
- ss-IGA score of 0 or 1 and a  $\geq 2$  grade improvement from baseline at Week 16 among participants with a baseline ss-IGA score  $\geq 2$
- $\geq 4$ -point improvement from baseline in PSSD itch score at Week 16 among participants with a baseline PSSD itch score  $\geq 4$
- PSSD symptom score of 0 at Week 16 among participants with a baseline PSSD symptom score  $> 0$
- PASI 75 response at Week 52 among PASI 75 responders randomized at Week 24
- PASI 90 response at Week 52 among PASI 90 responders randomized at Week 24

#### **4.3.1.3. Analysis Methods**

##### **4.3.1.3.1. Analytical Approaches for Main Estimands**

The efficacy analyses for key secondary endpoints will be based on the FAS or randomized at Week 24 analysis set by intervention group. The detailed methods of analysis and approach to control multiplicity is specified in Section 2.1.

##### **Binary Endpoint Analyses**

The binary key secondary endpoints will be analyzed using the main estimands described in section 4.3.1.2.1. Composite strategy will be used for ICEs 1, 2 and/or 4 (as applicable) where participants with those ICEs will be considered as non-responders and treatment policy strategy will be used for ICE 3 where observed data will be used. For the analysis at Week 52, participants experiencing an ICE 2 from Week 24 to Week 52 will be considered non-responders at Week 52, regardless of whether an ICE 2 occurred prior to Week 24. After the application of ICEs, participants with missing data will be imputed as non-responders. The proportions of participants achieving a key secondary efficacy response will be summarized and compared between treatment groups in the same manner as the co-primary endpoints using the appropriate stratification factors. For endpoints at or prior to Week 16, the stratification factors for randomization at baseline may be used in analyses. Geographic region may be removed as a stratification factor in CMH tests for endpoints with low response rates. For the analyses of PASI 75 at Week 52, stratification factors of PASI 90 response status at Week 24, and geographic region may be used in the analyses. A stratification factor of geographic region may be used for the analysis of PASI 90 at Week 52.

In addition, key endpoints at or prior to Week 16 (defined in 4.3.1.2.1) will be summarized and compared between treatment group among adolescent participants using a CMH test stratified by geographic region.

##### **Time to Event Analyses**

For the analyses related to the time to event endpoints (i.e., time to loss of PASI 75, time to loss of PASI 90) during the withdrawal period, composite strategy will be used for ICEs 1, 2 and 4 where participant with these ICEs will be considered as an 'Event' of loss of PASI response.

Treatment policy strategy will be used for ICE 3 where observed data after this ICE will be utilized in the analysis. The remaining missing PASI score after the Week 24 visit will not be imputed.

The life table method will be used to estimate the distribution of time to loss of PASI response for intervention group. The median time of loss of PASI response will be provided. The number and percent of participants who had a loss of response or were censored will be reported. In addition, the cumulative percent of participants who maintained a PASI response with 95% CI will be estimated by life table method after Week 24 (at 4 weeks, 8 weeks, and 12 weeks, etc.) and a survival curve (probability that participants maintain a PASI response) will also be plotted by intervention group.

The comparison of the distribution of loss of response between JNJ-77242113 and placebo group will be based on a stratified log-rank test. Hazard ratio and its 95% confidence interval will be estimated based on a stratified Cox's regression model with intervention as the explanatory variable. Stratification factors used in these analyses include PASI 90 response status at Week 24 (if applicable), and geographic region.

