1.3. Schedule of Activities (SoA)

1.3.1. Schedule of Activities – Screening Through Week 52

Period	Screen-ing	Placebo-controlled					JNJ-77242113 Treatment		Randomized withdrawal and retreatment						Unsch-eduled ^{a,b}	Notes: See Section 1.3.2 for Early Termination Visit procedures.
Week (W)	-5-0	0	2	4	8	12	16	20	24	28	32	36	44	52		
Visit Window (days)			±2	±2	±4	±4	±4	±4	±4	±4	±4	±4	±4	±4		
Study Procedure																
Screening/Administrative																
ICF/assent	X															Must be signed before first study-related activity.
ICF/assent for optional skin biomarker substudy	X															ICF/assent for optional substudies can be signed at the Week 0 visit before any related substudy assessment are performed.
ICF/assent for optional photography substudy	X															
ICF/assent for optional DNA/genomics substudy	X															
Demographics	X															
Medical history	X															Including psoriasis diagnosis.
Prestudy therapy	X															Review of medications, including previous psoriasis medications.
Inclusion/exclusion criteria (Section 5)	X	X														Minimum criteria for the availability of documentation supporting the eligibility criteria are described in Source Documents section of Appendix 2 . Check clinical status again before first dose of study intervention.
Chest imaging	X															Chest radiographs or CT ≤12 weeks before first administration of study

Period	Screen-ing	Placebo-controlled					JNJ-77242113 Treatment		Randomized withdrawal and retreatment						Unsch-eduled ^{a,b}	Notes: See Section 1.3.2 for Early Termination Visit procedures.
Week (W)	-5-0	0	2	4	8	12	16	20	24	28	32	36	44	52		
Visit Window (days)			±2	±2	±4	±4	±4	±4	±4	±4	±4	±4	±4	±4		
Study Procedure																
																intervention. This is optional for adolescent participants.
IGRA	X															Includes either QuantiFERON®-TB Gold Plus or T-SPOT® TB. In addition to IGRA, tuberculin skin test may be used to screen for latent TB if preferred by local health authorities or the investigator.
Hepatitis B and C serology	X															
HIV antibody test	X															
FSH	X															If needed to confirm postmenopausal status.
eDiary Compliance	X	X	X	X	X	X	X									Check eDiary completion and retraining of participants as necessary. Additional checks maybe performed as needed.
Study Intervention Administration																

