9.3.1. General Considerations

Simple descriptive summary statistics, such as n, mean, SD, median, interquartile range, minimum, and maximum for continuous variables, and counts and percentages for discrete variables will be used to summarize most data.

For binary endpoints, treatment comparisons will be performed using a CMH test stratified by age group at screening (adolescents <18 years and adults ≥18 years), baseline weight category for adults (≤90kg, >90kg) and geographic region. In case of rare events for binary endpoints, Fisher's exact test will be used. For repeated measure continuous endpoints, treatment comparisons will be performed using a MMRM model. The MMRM will include treatment, age group (adolescents <18 years and adults ≥18 years), baseline weight, geographic region and baseline value, as explanatory factors. The MMRM model will also include visit, treatment group by visit interaction, and baseline value by visit interaction as additional explanatory factors. The LS mean estimates and their corresponding 95% CI will be provided at each timepoint. In addition, the estimates of LS mean difference and 95% CIs between treatment groups will be provided. Analysis of

covariance will be used to analyze some continuous endpoints when appropriate. The ANCOVA will include treatment group, baseline value, weight, geographic region and age group. The LS mean estimates and their corresponding 95% CI will be provided. In addition, LS mean difference and 95% CIs between treatment groups will be provided. For time to event endpoints, treatment comparisons will be performed using a log-rank test stratified by baseline weight category for adults (≤ 90 kg, >90 kg), geographic region and age group. Kaplan-Meier or life-table estimates of cumulative rate by treatment group will be provided to evaluate the timing of event occurrence in different treatment groups.

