##### **4.3.1.1.2. Psoriasis Area and Severity Index (PASI)**

Refer to section 4.2.1.1 for details.

Meeting PASI 75 criteria: defined as having  $\geq 75\%$  improvement in PASI from baseline.

Meeting PASI 100 criteria: defined as having 100% improvement in PASI from baseline.

The time to loss of PASI 75 response through Week 52: PASI 75 response will be assessed at each visit between Week 24 and Week 52. Participants who experience a loss of PASI 75 response ( $< 75\%$  improvement from baseline) at any visit between Week 24 and Week 52 will be considered as having an 'event'. The time to loss of PASI 75 response is defined as the time from rerandomization at Week 24 to the visit of loss of PASI 75 response. Participants who do not experience any event between Week 24 and Week 52 will be censored at the last disease assessment visit or Week 52.

The time to loss of PASI 90 response through Week 52: similar to the definition of time to loss of PASI 75 response except using loss of PASI 90 response, which is when  $< 90\%$  improvement from baseline is observed.

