##### From Week 24 Through Week 52 – Randomized Withdrawal and Retreatment Period

###### Randomized Withdrawal period

- The Life table method will be used to estimate the distribution of time to loss of  $\geq 50\%$  of the Week 24 PASI improvement (i.e., time to retreatment) after withdrawal. The median time to loss of  $\geq 50\%$  of the Week 24 PASI improvement will be provided.
- The proportion of PASI responses (PASI 75, 90, and 100) will be summarized over time from Week 24 through Week 52 for participants randomized at Week 24.
- The change and percent change from baseline in PASI total score will be summarized over time from Week 24 through Week 52 for participants randomized at Week 24.

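### The life table does not suit visit-dated losses with censoring at Week 52: the Week 52 cumulative loss is wrong under every 4-week interval rule checked, in a direction the SAP leaves open

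*SAP*

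**What the plan says.** SAP 4.3.1.3.1 (Time to Event Analyses) names the estimator for the two key secondary time-to-loss endpoints: "The life table method will be used to estimate the distribution of time to loss of PASI response for intervention group". The same paragraph asks for a median, a survival curve, and the cumulative percent maintaining response with its 95% CI, "estimated by life table method after Week 24 (at 4 weeks, 8 weeks, and 12 weeks, etc".

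SAP 4.3.1.1.2 sets the data structure. Loss can be seen only at visits: "PASI 75 response will be assessed at each visit between Week 24 and Week 52". The event time is "the time from rerandomization at Week 24 to the visit of loss of PASI 75 response". Participants without an event "will be censored at the last disease assessment visit or Week 52".

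The method is carried further. SAP 4.3.2.3 analyses time to loss of IGA 0 or 1 in the same way, and SAP 4.4.2.5 uses it for time to retreatment: "The Life table method will be used to estimate the distribution of time to loss of" at least half of the Week 24 PASI improvement. The protocol is wider and allows either estimator: "Kaplan-Meier or life-table estimates of cumulative rate by treatment group will be provided" (9.3.1).

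No section gives the interval limits, says which interval takes a time that falls on a limit, or says whether time to event runs on nominal or actual visit dates. SAP 4.1.1 makes nominal visits the default for by-visit analyses only.

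**The concern.** The actuarial life table assumes that participants censored in an interval leave, on average, halfway through it, so it removes half of them from the number at risk. An event-free completer here was examined at Week 52 and was at risk for the whole last interval. If that censoring shares an interval with the Week 52 losses, the loss probability in the interval is nearly doubled when losses are few. If the interval limits instead put Week 52 in the next interval, the estimate read at Week 52 leaves those losses out. The reporting times of 4, 8 and 12 weeks also fall on visit times, so the rule at the limits matters there too.

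At stake are the percent maintained, its confidence interval and the curve, which describe durability for both key secondary time-to-loss endpoints, for loss of IGA 0 or 1 and for time to retreatment. They would sit beside crude counts from the same participants that do not agree with them.

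**Working it through.** **Inputs**
- Visits after Week 24: Weeks 28, 32, 36, 44 and 52, i.e. 4, 8, 12, 20 and 28 weeks, each with a ±4-day window (Protocol 1.3.1).
- Arm size: 540 adults × 2/3 = 360; × 75% responders = 270; 1:1 gives 135 per arm (SAP 1.2 and 5).
- Planned Week 52 PASI 75 response: 80 vs 60%, 85 vs 65%, 90 vs 70% (SAP Table 9). Cumulative loss is taken as 1 minus these. Loss at any visit could be higher.
- Assumptions, since the documents do not say how losses spread over visits: equal losses at the five visits, and no dropout. The Week 52 share is varied below.

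**The plan's own figure.** The documents give no cumulative-loss figure. The power for PASI 75 at Week 52 with 135 per arm (pooled-variance normal approximation, two-sided 0.05) is 95.2%, 97.0% and 98.7%, against the stated 95.2%, 97.0% and 98.6%. The inputs therefore reproduce.

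**Right-closed nominal intervals.** Week 52 losses d and censorings c share the last interval. With n at risk, the life table uses d/(n − c/2), whereas everyone was at risk and the correct value is d/n.
- True loss 20%: 27 losses, 5.4 per visit. At Week 52, n = 135 − 21.6 = 113.4, d = 5.4, c = 108. Correct: 5.4/113.4 = 4.8%. Life table: 5.4/(113.4 − 54) = 9.1%. Cumulative loss = 1 − 0.84 × 0.909 = 23.6%.
- True loss 40%: 54 losses, 10.8 per visit. n = 91.8, d = 10.8, c = 81. Life table: 10.8/(91.8 − 40.5) = 21.1%. Cumulative loss = 1 − 0.68 × 0.789 = 46.3%.

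**Left-closed nominal intervals.** A time of exactly 28 weeks falls in the next interval, so the estimate at 28 weeks covers only four of the five visits: 16% and 32%.

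**Actual days.** With jitter at Week 24 and at Week 52, about half of the Week 52 visits fall before 28 weeks. Working in proportions:
- 20%: 0.84 × [1 − 0.02/(0.84 − 0.20)] = 0.814, loss 18.6%.
- 40%: 0.68 × [1 − 0.04/(0.68 − 0.15)] = 0.629, loss 37.1%.

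Simulation with uniform ±4-day jitter gives the two actual-day rows below, depending on which interval takes visits exactly on the limit.

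| 4-week convention | True 20% | True 40% | Gap (true 20 points) |
|---|---|---|---|
| Nominal, right-closed | 23.6% | 46.3% | 22.7 |
| Nominal, left-closed | 16.0% | 32.0% | 16.0 |
| Actual days, left-closed | 18.3% | 36.3% | 18.0 |
| Actual days, right-closed | 19.0% | 37.8% | 18.8 |

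**Range for the half-count reading.** With q = d/n and S the true proportion maintained at Week 52, the excess is S × q/(1 + q). The Week 52 share of losses is varied from 5% to 29%; the upper value is 8/28, i.e. losses spread evenly over time.
- Continued arm: from +0.5 points (10% loss, 5% share) to +5.0 (20% loss, 29% share).
- Withdrawal arm: from +1.4 (30% loss, 5% share) to +8.3 (40% loss, 29% share).
- Gap between arms: 20.9 to 24.2 points against a true 20.

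**Earlier landmarks.** Under right-closed nominal intervals they are correct without dropout; with 2% dropout per interval (assumption) the half-count moves them by at most 0.3 points. Under left-closed nominal intervals each is one visit late, so loss at 4 weeks is 0% where the truth is 4%/8%. With left-closed intervals on actual days, loss at 4 weeks is about 1.8%/3.6%.

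**The case against.** The strongest reply is that the SAP does not commit to the faulty calculation. It names an estimator that the protocol permits and leaves the intervals to programming, so on this view there is only missing detail. It is true that no single error can be read off the SAP. But none of the four 4-week conventions checked returns the true Week 52 figure, so supplying a 4-week interval rule would not by itself cure it.

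A reader might infer that cumulative loss will be overstated by several points in both arms. The documents do not support that. Only one of the four conventions overstates at Week 52, and even there the continued-arm excess is below 2 points when losses are few or early. A reader might also pair the 23.6% at Week 52 with the 1.8% at 4 weeks, but these come from different conventions and cannot both occur in one analysis. Reading the actual-day curve at the end of its last interval gives about 26%/50%, but that point is 32 weeks after Week 24, i.e. Week 56, outside the withdrawal period.

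Two further replies stand. Not every event-free participant reaches Week 52: early dropouts are censored at their last assessment, and for people leaving between visits the actuarial adjustment has some rationale. And the damage is bounded. The summary measure for these endpoints is the hazard ratio (SAP Table 4), and the confirmatory test is a stratified log-rank test. Nor should the curve be expected to match PASI 75 at Week 52: that endpoint uses Week 52 status with missing data as non-response, while time to loss counts a loss at any visit, so the two would differ under Kaplan-Meier as well.

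**Conclusion.** The concern holds for the descriptive estimates only. With losses dated to visits and completers censored at the last of those visits, the life table gives a wrong Week 52 cumulative loss under each 4-week convention checked. The error ranges from about 4 points too low to 3.6 too high at a true 20%, and from about 8 too low to 6.3 too high at a true 40%. The sign depends on a rule that the SAP does not state. These sizes rest on equal losses at five visits, no dropout, loss equal to 1 minus planned response and, for the actual-day rows, the assumed jitter.

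The gap between arms can be widened (half-count reading) or narrowed (the other three), so a systematic tilt in favour of the product is not established. The log-rank test, Cox hazard ratio, crude numbers with loss or censored, and the binary Week 52 endpoints do not use the half-count, so no type I error or success claim is at risk. The median is affected only if the curve crosses 50% where the estimate is distorted; in the 20% and 40% scenarios with equal losses it is not reached at nominal times.

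**What to change.** In SAP 4.3.1.3.1 and 4.4.2.5, replace the life table with Kaplan-Meier. SAP 4.3.2.3 then follows by reference, and the life-table sentence in SAP 4.1 should be aligned. Specify:
- time on scheduled visits: 4, 8, 12, 20 and 28 weeks after Week 24;
- events ahead of censorings when both fall at the same visit;
- results reported at those visits only;
- events found at unscheduled visits, or defined by the date of ICE 1 or ICE 2, assigned to the next scheduled visit.

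Under the assumptions above, this returns 20% and 40% exactly. Protocol 9.3.1 already permits Kaplan-Meier, so no protocol change is needed. The cost is SAP wording and a programming option. The one downside is small: the mapping rule slightly coarsens the timing of events dated between visits.
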